 - If a woman seroconverts while on PrEP, there may be a risk of ART resistance, though research has demonstrated that the risk of ART resistance is very low [12, 13]. In the case of seroconversion, Drs [name] and [name] will follow seroconverters with the study team to evaluate if the patient achieves viral suppression within 6 months of ART start, and if not, she will be referred for specialist attention for testing for ART resistance and clinical follow-up.

Adverse events:

- **Maternal adverse events:** We will collect data on maternal adverse events by asking mothers about intercurrent medical events, which will be reviewed by an obstetrician, including any hospitalizations or illnesses. We will also track and report changes in creatinine or other toxicities in women on PrEP.
- **Infant adverse events:** We will collect data on infant adverse events by asking mothers about infant health or intercurrent medical events, which will be reviewed by a pediatrician.
 - Adverse birth outcomes will include infants that were small for gestational age, pre-term births, miscarriage and stillbirths.

Table 1: PrEP-PP cohort measures by participant study month

Participant study month	Pregnancy						Post-partum											
	1	2	3	4	5	6	7	8	9	10	11	12	13	14	15	16	17	18
Study enrollment and consent of consecutive sample of HIV-negative pregnant women (N=220)	X																	
PrEP group, individual (or couples counseling where applicable) and information, education, counseling materials on PrEP in pregnancy and breastfeeding in local languages (at each visit)	X	X	X	X	X	X	X		X		X		X		X			X
Routine ANC and postnatal care, well-baby visit follow-up (as available in standard of care), including rapid HIV testing, pregnancy, and birth outcomes	X	X	X	X	X	X	X		X		X		X		X			X
ACASI survey to collect: behavioral acceptability, knowledge, and substance use data	X	X	X	X	X	X	X		X		X		X		X			X
Screening at enrolment for Hepatitis B surface antigen. If HBsAg+ = excluded from study	X																	
Laboratory testing for STIs (chlamydia and gonorrhoea) & treatment if positive	X				X		X											
For women on PrEP:																		
Laboratory tests of creatinine (if eGFR<60ml/min cannot continue on PrEP, refer to return in 1 month for re-test)	X			X			X								X			X
PrEP pharmacy refills and adherence supportive counseling monthly (for first 3 months on PrEP) then every 2 months for following months	X	X	X		X		X		X		X		X		X			X
DBS taken for TDF-DP adherence measures (bi-monthly in participants on PrEP)	X	X	X		X		X		X		X		X		X			X
In-depth interviews for 20 participants							X											X
Collect study data on: (1) PrEP counseling, (2) PrEP medication when requested, (3) regular appointments, (4) IEC materials, (5) adherence counselling and support by facility, through patient ACASI survey at every study visit	X	X	X	X	X	X	X	X	X	X	X	X	X	X	X	X	X	X

Training, quality assurance and supervision:

1. *Existing DOH staff:* We will conduct an on-site half day training for existing counselors, nurses and midwives and Managers in the two study sites on the study protocol to ensure that they understand and support the integration of the study in their facility.

- a. **Inclusion of interviews for healthcare providers in health facility to understand their knowledge of and attitudes around PrEP:** We seek to interview existing health care providers including nurses, counselors, midwives and managers to understand their knowledge about PrEP, HIV prevention in pregnancy and any attitudes about PrEP that may affect future integration of

PrEP and PrEP uptake in the facility. We will interview approximately 20 health care providers and have one focus group in those providers in isiXhosa or Afrikaans. We will record, translate and transcribe their responses and analyze the results thematically in order to develop interventions around provider training and support.

2. *Study staff:* We will hire 2 counselors, 2 nurses, 2 coordinators who will receive a 3-day training program and they will be required to complete the entire training course. After completion of the training, the study PI will observe the counselor and nurse completing each step of the intervention with a mock patient. Upon satisfactory completion of observed sessions, the counselors and nurses will be certified to conduct the study intervention and will receive a completion certificate.
3. *Quality assurance* will occur on three levels. Day-to-day monitoring, supervision, and support of counselors will be carried out by the Study Coordinators (from UCT—1 per facility). The Study Coordinator will provide on the job training to ensure that counselors and nurses respect the study protocol. Adherence to the counseling protocol will be established by the Study Coordinator who will sit in on a random subsample of 20% of counseling sessions to ensure that counselors are adhering to study protocols.

Sources of data

There are four sources of data/materials for this trial: (1) survey measures (ACASI); (2) in-depth interview measures in 20 randomly selected women (n=10 who were on PrEP compared with 10 not on PrEP); (3) laboratory measures; and (4) information abstracted from routine care records, including related to PrEP. The collection of data materials will be conducted by a study measurement team comprised of one study coordinator, one study interviewer, and one fieldworker. All procedures for data collection (regardless of source) will be outlined in a study manual of procedures, with individual activities guided by standard operating procedures (e.g., DBS, specimen transport, or questionnaire administration).

Survey measures (ACASI)

At study measurement visits, questionnaires will be administered to mothers participating in the study using ACASI on a tablet with a site coordinator available for troubleshooting. ACASI will help reduce the amount of respondent bias when responding to sensitive questions around sex and substance use. Following standard procedures, the questionnaires will be translated into isiXhosa and Afrikaans and back translated to ensure appropriate phrasing. Questionnaires will include:

- Basic demographic information and obstetric history (enrollment only)
- Partner's HIV status
- Sexual behaviors in the past month and week including # of sex partners, type of sex, and frequency of sex and condom use
- Substance use information using the AUDIT-C and DAUDIT scales
- Risk perception scales
- Partner, community and social support for PrEP
- For PrEP users, questions related to PrEP adherence according to self-report (the 3-day and 1-month recall and a visual analog scale) and pharmacy-based pill counts will be conducted at each study measurement visit.
- Additional schedules will be used to collect data on symptoms in mothers that are potential side-effects of PrEP use (at all study visits)
- We will also use short questionnaires to collect data on all women's experiences in the study, and the acceptability of the PrEP initiation, including what kind of services were offered at each visit (e.g. counseling, peer mentorship, and IEC materials, medication)
- Self-reported symptoms related to STIs

- This will focus on the positive and negative aspects of their experiences of PrEP initiation in pregnancy and breastfeeding and any factors associated with PrEP initiation, retention, and adherence.

Interview measures

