Our team is comprised of highly experienced adolescent HIV prevention researchers, including [name] and [name], who have a long history of research that seeks to address the key health issues facing South African adolescent girls while at the same time protecting this vulnerable population. The research sites have considerable experience in conducting clinical research in adolescent populations.

Figure 2. HIV incidence (%) by age and sex in South Africa

[figure not shown]
[figure not shown]

Figure 3. Adolescent pregnancy in South Africa, 2010-2013

Our study, PrEP-PP (PrEP in Pregnant and Postpartum women) will determine the distribution of women across the PrEP cascade (i.e. PrEP initiation, retention, and adherence) in a cohort of HIV- pregnant and breastfeeding adolescent girls and women in two public health facilities in South Africa to inform policymakers about the efficacy of PrEP integration into antenatal (ANC) and postnatal care in high HIV incidence communities.

2. Study objectives:

The objectives of the study are to:

1. Determine the distribution of women across the PrEP cascade:
 - (1) Evaluate the proportion of pregnant and breastfeeding women who initiate PrEP out of all women offered PrEP
 - (2) Evaluate the proportion of pregnant and breastfeeding women who are retained in the PrEP cohort
 - (3) Evaluate the proportion of pregnant and breastfeeding women who initiate PrEP who adhere to PrEP using objective dried blood spot measures and subjective measures of self-reported pill count and adherence
 - (4) Evaluate the proportion of pregnant and breastfeeding women on PrEP (and not on PrEP) who acquire HIV, who transmit HIV to their infant, and who report adverse events
2. Evaluate patient and provider-level factors associated with the PrEP cascade using quantitative and qualitative approaches (including in-depth interviews)

3. Study design

To address these objectives, we will conduct an observational cohort study in 220 pregnant women who will be recruited at the first antenatal care (ANC) visit from the Gugulethu Midwife Obstetric Units in Cape Town. We will follow the enrolled women through 12-months post-delivery.

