Setting. The study will take place in two urban townships in Cape Town (Gugulethu MOU) with high HIV incidence that span the different socioeconomic, cultural, and ethnic groups in South Africa. We selected this community because of the high HIV prevalence there in pregnant and breastfeeding women, and because of the high number of mothers visiting every month for ANC and labour/delivery. Further, our team has several years' experience implementing research studies in those MOUs which will facilitate the integration of the study there. In 2017, Gugulethu saw over 3300 new ANC consultations per month, and 72% (n=2300) are HIV-negative. Considering our experience and patient flow, we are confident that at least 60 women/month per facility can be enrolled. Further, Drs. [name], [name] and colleagues have conducted research in the Gugulethu community for more than a decade and have substantial experience partnering with local health services. Building on this platform, we will use existing infrastructure in each clinic, including capacitating existing clinical providers, pharmacists and counselors, to provide PrEP care to pregnant and breastfeeding mothers. We will hire study staff to assist in the coordination, data management, and overall quality assurance of the counseling, drug provision and participation follow-up.

4. Study population

Study counselors will enroll consecutive eligible, consenting pregnant adolescent girls (≥ 16 years) and women in ANC (N=220 pregnant women) and follow them up for 12-months postpartum or until censorship for a mean of 18-months' follow-up.

Inclusion Criteria:

1. ≥ 16 years old
2. confirmed HIV-negative (using 2 rapid HIV test kits, confirmed with a 4th generation antigen HIV test),
3. lives within 20 kilometers of a clinic

4. confirmed to be pregnant
5. without psychiatric or medical contraindications to PrEP

Exclusion criteria:

Individuals not meeting the above criteria or meeting any of the following criteria will be excluded:

- Concurrent enrolment in another HIV-1 vaccine or prevention trial
- Medical hospitalization in the past year for any reason
- Receipt of TB treatment within the past 30 days
- History of renal disease
- Exhibiting psychotic symptoms (including hallucinations, suicidal or homicidal ideations, or violent behaviour)
- Currently or history of taking an anti-psychotic medication (such as for treatment of bipolar disorder, schizophrenia, or postpartum psychosis following a previous pregnancy)

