Step 1: Health care providers in Gugulethu MOU provide group counseling to women at their first ANC visit, beginning with a session orientation, so that the patients know what to expect from the ANC service. This includes information about HIV testing and counselling, ART treatment for PMTCT, and the importance of HIV prevention for those women who test HIV-negative. The counselor will also be trained to provide simple information about PrEP, including what PrEP is, its benefits and risks, and the importance of daily adherence. The counselor will discuss the side effects that may occur in the first 1-2 weeks (similar to new ART patients) and will answer any questions about PrEP in the group setting.

Step 2: Following the South African National guidelines, patients privately receive pre-test counseling for HIV, including conducting a risk assessment and assessing her level of concern about having HIV. A discussion follows about the client's most recent risk exposure or behavior before and during pregnancy. The patient again is counseled about how best to reduce the risk of acquiring HIV

during pregnancy (and increased risk of MTCT), including previous risk reduction attempts, successful experiences in using condoms, knowledge of partner's serostatus, obstacles to risk reduction, and triggers and situations that increase the likelihood of high-risk behavior.

Step 3: Disclosure of HIV negative result and post-test counseling. The counselor shows the client the actual results on the test kit, and then explores the client's reactions to the test results. Additional counseling will be provided with information about PrEP if the woman is diagnosed HIV-negative.

Step 4: The counselor explains that the mother may be eligible to participate in a study of HIV prevention in pregnancy and breastfeeding periods, including PrEP for women who decide they want to take it. The counselor will review the benefits and risks of using PrEP and participating in the study and will conduct a screening questionnaire.

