Step 5: If the client agrees to participate in the study (*she does not have to agree to take PrEP*), she will be referred to the study recruiter on site who will bring the mother to the Green Clinic in Gugulethu (study site) where the study counselor will evaluate study eligibility (see study inclusion, exclusion criteria), read the consent form and ensure that she understands the study design and consent form before signing, asking questions to ensure comprehension.

Infant consent form: The participant will review and sign the infant consent form when she returns for her first post-partum visit with her infant.

Step 6: STI testing: Participants will self collect a vaginal swab that will be tested for baseline STIs (chlamydia, gonorrhea and trichomonas vaginalis) using Cepheid® point of care testing (will run during interview and PrEP counseling—steps 7-9). Participants will be treated if diagnosed with a STI according to National Guidelines. They will receive a partner notification letter to bring their partner in for treatment as well.

Step 7: All participants will be provided with a tablet to complete her audio computer assisted survey instrument (ACASI) baseline survey, which may take approximately 20- 30 minutes to complete.

Step 8: All participants will watch a video about PrEP (adapted from existing video from [name] ongoing PrEP studies in Cape Town), followed by a Q&A session with the study counselor.

Step 9: The participant will receive individual counseling about HIV prevention in pregnancy including PrEP. Risk reduction counseling will be provided for all women and will include:

- Consistent and correct use of condoms
- Knowing your status and partner's status
- If partner is HIV infected, should be on ART and achieve viral suppression
- Use of drugs and alcohol increases risk of HIV

Step 10: For all participants, the study nurse will draw blood to test for baseline creatinine tests and Hepatitis B.

- If woman is HebBsAG + she will be excluded from the study
- Women with low creatinine can participate in the study but can only receive PrEP if their eGFR >60mL/min
- The turnaround for renal function tests will be 24-48 hours. We will call participants who have started PrEP to return if their creatinine results are abnormal. They will be

requested to stop taking PrEP until their creatinine results return to normal and will be able to re-test the following month.

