The primary analysis will focus on measuring the distribution of women across the PrEP cascade including: initiation, retention and adherence. **PrEP initiation** will be based on a woman’s uptake of PrEP and allow for stoppage and re-initiation; **PrEP retention** will be defined as not missing >1 visit among those on PrEP (with separate analyses of PrEP stoppage). For **PrEP adherence** for women on PrEP we will measure both **perfect adherence** (i.e. level of objective adherence throughout pregnancy and breastfeeding periods) as well as “**prevention-effective**” adherence (i.e. adherence before and during times of sexual activity) in participants through objective and subjective measures to evaluate agreement between the two measures, and the level of under- or over-reporting. Primary adherence analyses will use objective measures (TDF-DP from DBS) taken on all those who enrolled and initiated PrEP; subsidiary analyses will consider (i) other adherence measures and (ii) multiple imputation for missing adherence data.

- **Use of PrEP will be measured** through alternate definitions of the main outcomes (e.g. adherence by self-report versus adherence by pharmacy refill), compared using measures of agreement and will be analyzed as independent models to contrast estimated associations.

- **Measurement of prevention-effective execution:** Execution refers to PrEP adherence during a time when at-risk sex happens. It is calculated by: number of doses reported, or recorded/number of expected doses based on HIV risk and PrEP initiation/discontinuation
- **Prevention-effective continuation:** Prevention-effective continuation describes the duration of PrEP use during periods of HIV risk and references the absolute time of use during pregnancy and breastfeeding periods. We will adapt the methodology from previous PrEP studies in SA including FEM-PrEP to create a semi-ordinal composite adherence score from blood specimens from DBS every 2-months.

Table 2: Study measures for PrEP-PP

Primary Outcomes	Measurement	Source	Frequency
PrEP initiation	# of women who initiate PrEP over time / total # of women in active cohort = proportion of women who initiate PrEP	Electronic provider log (REDCap)	Daily entry, weekly analysis

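### Initiation is measured among women who joined the study, not among all women offered PrEP, and the plan specifies no count of those who declined to join

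*Combined protocol and SAP*

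**What the plan says.** Section 2 (Study objectives), objective 1(1), is to "Evaluate the proportion of pregnant and breastfeeding women who initiate PrEP out of all women offered PrEP". Section 6, Table 2, makes initiation the first primary outcome and defines it as the number "of women who initiate PrEP over time / total # of women in active cohort = proportion of women who initiate PrEP", taken from the electronic provider log.

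Section 4 describes how that cohort is formed: "Study counselors will enroll consecutive eligible, consenting pregnant adolescent girls" and women. Section 5 gives the order of events at the first antenatal visit:

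- Step 1, group session, before any consent: "The counselor will also be trained to provide simple information about PrEP, including what PrEP is, its benefits and risks".
- Step 3, post-test counselling: women who test HIV-negative get further information about PrEP.
- Step 4, study invitation: "The counselor explains that the mother may be eligible to participate in a study of HIV prevention in pregnancy and breastfeeding periods, including PrEP". The counsellor reviews benefits and risks and runs a screening questionnaire.
- Step 5: "If the client agrees to participate in the study", she goes to the study site for eligibility assessment and consent. The introduction to Section 5 likewise says that interested women go on to the study trailer.
- Step 11: participants are asked whether they want to start PrEP that day, and the answer is recorded.

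No outcome in Table 2 and no analysis in Section 6 uses the number of women invited, ineligible or declining.

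**The concern.** The objective and the outcome definition refer to different groups. Every HIV-negative woman who goes through Steps 1 to 4 has heard what PrEP is, what it may do for her and what it may cost her. The uptake question is recorded only for those who then agreed to take part in research. A woman who says no at Step 4 because she does not want PrEP is a non-acceptor in the ordinary sense, yet she appears in neither numerator nor denominator.

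Initiation is the first step of the cascade, and the stated purpose is to inform policymakers about PrEP within antenatal and postnatal care. A reader of the results would naturally take the proportion as uptake among antenatal attendees offered PrEP. If joiners and decliners differ in their wish for PrEP, the two quantities differ, and without a count taken at the time of invitation the gap cannot be sized.

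**Working it through.** The documents give no expected uptake, consent share or precision for initiation, so there is no planned figure to reproduce. The patient-flow figures in Section 3 (about 2300 HIV-negative women a month; at least 60 enrolled a month per facility) describe throughput and capacity, not the share of invited women who agree.

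**Inputs.** From the documents: n = 220 enrolled. Assumed and varied:

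- p = uptake among participants
- q = share of invited women who consent
- d = uptake that decliners would have had

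**Formulas.**

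- Uptake among all invited = pq + (1−q)d
- Overstatement by the cohort figure = p − [pq + (1−q)d] = (1−q)(p−d)
- Bounds with no assumption on d: pq (d = 0) to pq + (1−q) (d = 1)

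**Size for p = 70%** (154 of 220 start):

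| q | Women invited, 220/q | pq | pq + (1−q) | Overstatement if d = 0 |
|---|---|---|---|---|
| 95% | 232 | 66.5% | 71.5% | 3.5 points |
| 90% | 244 | 63% | 73% | 7 points |
| 80% | 275 | 56% | 76% | 14 points |
| 70% | 314 | 49% | 79% | 21 points |
| 50% | 440 | 35% | 85% | 35 points |

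**Compared with sampling error.** The 95% half-width at p = 70% is 1.96 × √(0.7 × 0.3 / 220) = 6.1 points. With d = 0 the overstatement passes this once q falls below about 1 − 0.061/0.70 = 91%. The comparison depends on p:

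- p = 50%: half-width 6.6 points; overstatement 5 points at q = 90% (smaller) and 10 points at q = 80% (larger).
- p = 90%: half-width 4.0 points; overstatement 9 points at q = 90% and 18 points at q = 80%.

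**Direction** (p = 70%, q = 80%):

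- d = 30%: 0.2 × (0.7 − 0.3) = 8 points too high.
- d = 70%: no bias.
- d = 90%: 0.2 × (0.7 − 0.9) = 4 points too low.

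The sign therefore depends on d alone, and the documents say nothing about d.

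**The case against.** The best defence is that Steps 1 to 4 give information and a study invitation, and that the only real offer of drug is the Step 11 question, repeated at follow-up to women not on PrEP. On that reading the women offered PrEP are the enrolled women, and Section 2 does place the cascade within a cohort. This is a possible reading, but the documents never define the offer that way, and the counselling before consent is specific to PrEP. If it is the intended reading, the objective should say so.

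A reader might infer that the cohort is selected on the outcome itself. The documents do not support that. The Step 4 invitation describes the study as "including PrEP for women who decide they want to take it", Step 5 says agreement to PrEP is not required, women who decline PrEP are kept in a deferred arm, and each visit brings reimbursement of up to R250. STI testing and hepatitis B screening are further reasons to join that have nothing to do with PrEP. Nor do repeated blood draws clearly deter women who do not want PrEP: follow-up creatinine and dried blood spots are described mainly for women on PrEP.

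It would also go too far to say that refusals will not be recorded. The screening questionnaire is completed before agreement, and a manual of procedures is to hold operational detail. What can be said is that the plan specifies no such count and uses none.

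Finally, any consented cohort is self-selected, and Section 6 calls this a formative pilot. That excuses limited power for comparisons. It does not remove the mismatch, because the same section says the pilot will provide estimates of the cascade.

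**Conclusion.** The mismatch stands on the text. Objective 1(1) names all women offered PrEP, Table 2 measures enrolled women, and no count of decliners links the two. The planned figure is uptake among study participants.

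That it overstates uptake among all women told about PrEP is plausible, not established; it requires decliners to want PrEP less often than joiners. The size is unknown because the consent share is not given. In the illustration with 70% uptake among participants and none among decliners, the gap is 7 to 35 points for consent shares from 90% down to 50%, larger than the 6.1-point sampling half-width. With smaller differences between joiners and decliners, or consent above about 91%, it is within sampling error. The point merits a change because the count must be taken prospectively and costs little.

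**What to change.** 1. At Step 4, use the existing screening questionnaire to keep an anonymous tally of HIV-negative women told about PrEP and the study, those ineligible on the questionnaire, those declining (with reason, including that they do not want PrEP), and those consenting.
2. Label the Table 2 proportion *among study participants*.
3. Report a second proportion for objective 1(1): initiators over all women eligible on the Step 4 questionnaire, with decliners counted as not starting. State two limits beside it: hepatitis B and creatinine results are known only after consent, so eligibility here means eligibility on the questionnaire; and declining the study is not the same as declining PrEP. Show women excluded after consent on a separate line, so that p and q refer to the same women.
4. Give pq to pq + (1−q) as the bounds that need no assumption about decliners. Do not present pq and p as bounds without qualification: p is an upper limit only if decliners would start no more often than joiners. At p = 80% and q = 70%, for example, the bounds are 56% to 86%, not 56% to 80%.

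The cost is a small recording task on a form already in use and one more row in the results. The second uptake figure will look less favourable than the first. No treatment or study visit changes.
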